4.5 Monitoring for Subject Compliance

Subjects or their caretakers will administer study medications according to the IP dosing instructions and training provided, ie; as close as possible to 8 a.m. and 8 p.m. Compliance will be assessed at each visit by asking the subject for their recollection about any missed doses. Confirmation of compliant IP dosing the evening prior to a study visit must be confirmed or the visit should be rescheduled. If the subject reports missing more than 4 doses since the prior visit, a Protocol Deviation will be documented and the subject will be counseled on IP compliance.

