1.4 Dose Rationale

Ocular PK data in rabbits and monkeys confirmed that H-1337 exhibits dose-related effects and can reduce IOP for upwards of 8-12 hours. The clinical doses, treatment period (28 days), and dosing regimen (BID) are expected to have an acceptable safety profile and have been selected based on preclinical toxicology data. The total daily administered dose of H-1337 in human subjects will be approximately 1.72 mg/day (or 0.03 mg/kg/day based on a 60-kg individual) when administered twice daily in both eyes at the maximal concentration of 1.0%. In a previous clinical study, 3 concentrations of H-1337 Ophthalmic Solution (0.06%, 0.02% and 0.6%) dosed twice-daily (b.i.d.) provided similar ocular hypotensive outcomes. In the present study, a high concentration of 1.0% is planned to be used both once (q.d.) and twice (b.i.d.)-daily. The dose is supported by preclinical safety studies. The highest dose from the previous study (0.6%, b.i.d.), as well as a positive marketed control, timolol ophthalmic solution 0.5%, b.i.d., will be included for comparison.

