3. STUDY DESIGN

3.1 Study Design

The trial will evaluate the safety and efficacy of 3 dose regimens of H-1337 (0.6% b.i.d., 1.0% b.i.d. and 1.0% q.a.m., and timolol maleate (0.5%, b.i.d.) OU for 28 days (\pm 2-day allowable window for Day 28).

Approximately 200 subjects will be randomized and dosed for 28 days. The parallel group, double-masked, active-controlled study will include the following dosing cohorts:

- H-1337 0.6% Ophthalmic Solution b.i.d. (n=50)
- H-1337 1.0% Ophthalmic Solution b.i.d. (n=50)
- H-1337 1.0% Ophthalmic Solution q.a.m. and H-1337 placebo q.p.m. (n=50)
- Timolol 0.5% Ophthalmic Solution b.i.d (n=50)

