IP Administration and Compliance: The first dose of study IP will be administered by study staff after the IOP measurement at T₀ on Day 1. Subjects will self-dose for the remainder of the trial except on study visit days when subjects will be instructed to refrain from self-dosing prior to the visit and the study morning IP will be administered by the unmasked dosing coordinator after the related IOP measurements; evening IP will be self-dosed (out of view of study staff) after the related IOP measurements. Compliance will be assessed at applicable visits by asking the subject their recollection of any missed doses. Confirmation of compliant IP dosing the evening prior to a study visit must be confirmed or the visit should be rescheduled. If the subject reports missing more than 4 doses since the prior visit, a Protocol Deviation will be documented and the subject will be counseled on IP compliance.

Heart Rate and Blood Pressure (BP) Measurements: Both systolic and diastolic blood pressure should be recorded. The same type of device and cuff must be used throughout the study on the same subject. An appropriate cuff size with a bladder encircling at least 80% of the upper arm should be used to ensure accurate measurements.

Blood pressure will be measured using the most ideal conditions possible given the subject's medical condition and age. If possible, the same arm should be used throughout the study. Blood pressure should be measured after sitting in a seated position for 5 minutes. Heart rate measurements will be measured by radial pulse for at least 30 seconds. The subject should be in a seated and relaxed state. An automated blood pressure unit may be used to measure the heart rate.

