4.10 Treatment Exposure

The number and percentage of subjects by number of missed doses will be summarized by eye and treatment. In addition, the number of missed doses will be summarized by eye and treatment using summary statistics for continuous variables.

Duration of drug exposure is defined as the number of days a subject receives an IP dose. The number and percentage of subjects in each category will be summarized by eye and treatment. The categories are: <7 days, 7 to <14 days, 14 to <21 days, 21 to <28 days, ≥28 days.

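### The pre-visit dosing check confirms only the previous evening's dose, which is placebo in the q.a.m. arm, so it secures recent active drug at Pre-T0 in three arms but not in that one

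*Protocol*

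**What the plan says.** **The condition for holding a visit.** Protocol 4.5, repeated under IP Administration and Compliance in Section 5, states: "Confirmation of compliant IP dosing the evening prior to a study visit must be confirmed or the visit should be rescheduled". No other dose is a condition of the visit.

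**What the evening dose contains.** Timolol and the two H-1337 b.i.d. regimens have an active evening dose. The third H-1337 regimen does not (Protocol 3.1: "H-1337 1.0% Ophthalmic Solution q.a.m. and H-1337 placebo q.p.m. (n=50").

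**The clock.** Doses are to be taken "as close as possible to 8 a.m. and 8 p.m". On visit days "subjects will be instructed to refrain from self-dosing prior to the visit and the study morning IP will be administered by the unmasked dosing coordinator"; this office dose comes only once the pressure has been read. The Pre-T0 reading therefore always reflects doses taken on earlier days.

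**The other compliance check.** At each visit subjects are asked to recall any missed doses. Sections 5.1.4 and 5.1.5 list this step before tonometry, and Section 5 asks that procedures follow the listed order. The consequence attached to it is: "If the subject reports missing more than 4 doses since the prior visit, a Protocol Deviation will be documented", with counselling. The count does not separate morning from evening doses.

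**Reporting.** SAP 4.10 summarises missed doses by eye and treatment and adds: "Duration of drug exposure is defined as the number of days a subject receives an IP dose". The placebo is listed among the investigational products in the synopsis.

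**The concern.** The reschedule rule shows that the sponsor wants the last dose before the Pre-T0 reading to have been taken. In three arms the rule does that. In the q.a.m. arm it confirms a placebo drop, and the last active dose, due the previous morning, can be missed without moving the visit. The same safeguard therefore protects the comparator but not this test arm.

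Day 28 Pre-T0 is a primary time point in both the protocol's set of 7 and the SAP's set of 9. In row 3 of the testing sequence (q.a.m. against timolol, 1.5 mmHg) every point must pass. Failure there stops rows 4 to 6, and rows 4 and 5 are the 1.0 mmHg tests of the two b.i.d. regimens. A lapse in morning dosing in one arm could thus close off claims for other arms. It would also blur the once-daily against twice-daily reading of the 1.0% strength, which Protocol 1.4 sets out as part of the design.

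**Working it through.** The plan gives no figure on this point, so there is none to reproduce.

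**Step 1: hours since active drug at Pre-T0.** Inputs: doses at 8 a.m. and 8 p.m. (Protocol 4.5), Pre-T0 at about 8 a.m. before the office dose (Section 5), evening-before dose confirmed.

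- b.i.d. and timolol arms: 8 p.m. to 8 a.m. = 12 h, however many mornings were missed.
- q.a.m. arm with *m* consecutive mornings missed up to the visit: 24 × (1 + *m*) h.

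| Consecutive mornings missed | b.i.d. and timolol | q.a.m. |
|---|---|---|
| 0 | 12 h | 24 h |
| 1 | 12 h | 48 h |
| 2 | 12 h | 72 h |
| 3 | 12 h | 96 h |
| 4 | 12 h | 120 h |

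The first row is the regimen itself. The gap in the check concerns only the time beyond 24 h. Four missed doses still do not exceed the deviation threshold, so even the last row triggers nothing stated.

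**Step 2: what the threshold means by arm.** Day 14 to Day 28 covers about 14 days. Four missed mornings are 4 of 14 active doses (29%) in the q.a.m. arm and 4 of 28 (14%) in a b.i.d. arm.

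**Step 3: which readings are affected.** Pre-T0 at Days 7, 14 and 28. Later Day 28 readings follow a supervised office dose, which is active in every arm. Day 1 precedes any missed dose.

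**Step 4: illustrative size.** Shift in the q.a.m. minus timolol mean at Pre-T0 = share who missed the previous morning × effect lost beyond 24 h. Neither input is in the documents.

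- Assumed 3-10% and 1-4 mmHg: 0.03 × 1 = 0.03 to 0.10 × 4 = 0.4 mmHg.
- Wider assumption, 2-20% and 1-4 mmHg: 0.02 to 0.8 mmHg.
- If no effect remains at 24 h, the loss and the shift are both 0.

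**Step 5: effect on passing that one time point.** Inputs: SD 3.0 and 45 per arm (SAP 3.3), upper limit of the two-sided 95% CI below 1.5 (SAP 4.3), and an assumed true difference of 0. SE = 3 × √(2/45) = 0.632. Half-width = 1.987 × 0.632 = 1.257. The point passes if the estimate is below 1.5 − 1.257 = 0.243.

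| Shift (mmHg) | (0.243 − shift)/0.632 | Chance of passing |
|---|---|---|
| 0 | 0.38 | 65% |
| 0.2 | 0.07 | 53% |
| 0.4 | −0.25 | 40% |

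The 65% start reflects the 1.5 margin and the two-sided 95% interval. The sample-size section instead uses 2 mmHg and a one-sided 5% test, so this does not contradict its 90%.

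**The case against.** The strongest reply concerns size. A fully adherent q.a.m. subject is already 24 h from active drug at Pre-T0. Protocol 1.4 reports, from rabbits and monkeys, that H-1337 "can reduce IOP for upwards of 8-12 hours". If little effect remains at 24 h, little more can be lost by 48 h, and a 4 mmHg loss would need at least 4 mmHg of residual effect at 24 h, which no passage supports. The quoted phrase sets no ceiling and is not human data, so the question stays open, but the low end of the range cannot be dismissed. The pass probabilities are equally conditional: if the true Pre-T0 difference were 1.0 mmHg, the chance of passing would already be about 12% ((0.243 − 1.0)/0.632 = −1.20), and the regimen's own trough would dominate. This objection stands and limits the severity.

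The reach is also narrow: one primary time point in row 3, and only once rows 1 and 2 have passed. The expected bias runs against H-1337, so it does not favour a false non-inferiority claim.

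A reader might infer more than the documents support:

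- *That 48 h is the limit.* It is the one-missed-morning case; the rule sets no cap.
- *That nobody asks about the morning dose.* Recall of any missed dose comes before tonometry, and noncompliance is a possible ground for withdrawal from treatment (Protocol 4.3). What is missing is a link from a missed morning dose to the visit.
- *That only the q.a.m. arm can be affected.* A b.i.d. or timolol subject who skipped the previous morning also passes the check. That subject has still had active drug 12 h earlier, so the effect is differential rather than exclusive.
- *That four missed doses mean four days off drug in one arm and two in the others.* This compares mornings only with consecutive doses. The like-for-like contrast is the share of active doses in Step 2.

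Finally, the ITT analysis is meant to hold whatever the adherence, and a stricter check moves readings away from ordinary use. But the plan has already chosen to control the last dose before the visit; the issue is that it does so unevenly.

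**Conclusion.** The asymmetry is real and follows from the documents alone: the visit condition secures about 12 h since active drug in three arms and nothing about active drug in the q.a.m. arm. No other provision closes it. Recall moves no visit, and the per-protocol exclusion of data points is discretionary with no criterion for this case.

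Its size is unknown. The 0.03-0.4 mmHg range and the fall from 65% to 53% or 40% rest on assumed shares, an assumed loss beyond 24 h and a true difference of 0. The documents do not show that the q.a.m. comparison would fail for this reason, and the effect may be negligible. The point is worth acting on because the expected bias has one direction, falls on a time point that must pass, and is cheap to remove. SAP 4.10 is a smaller, descriptive matter: a day with only the evening placebo counts as exposure, but that table feeds no test.

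**What to change.** Reconcile the compliance check in Protocol 4.5 and Section 5 with the placebo-evening regimen in Protocol 3.1:

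- Confirm that both the a.m. and the p.m. dose of the day before the visit were taken, for every subject in all arms, under the existing reschedule rule and within the existing visit windows. Asking everyone the same question leaves masking intact.
- Record missed doses separately for the a.m. and p.m. bottles.
- In SAP 4.10, report missed doses and exposure for the q.a.m. arm on the a.m. (active) bottle.

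No dose or regimen changes. The cost is one question at a check already made at Days 7, 14 and 28, one CRF field and a few words in the SAP. The downside is slightly more rescheduling, with some risk that a Day 28 visit falls outside its ±2-day window; since missing values are not imputed, a lost visit would not be filled in. Unless missed doses are recorded by bottle, q.a.m. exposure to active drug cannot be reconstructed afterwards.

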4.6 Lifestyle Guidance

During the study, subjects of childbearing potential (who are menarchal) must use reliable precautions to prevent pregnancy. These restrictions should be followed throughout the duration of the study and maintained for 30 days after trial completion.

Acceptable contraceptive methods for subjects of child-bearing potential:

Abstinence

- Hormonal methods of contraception (including oral and transdermal contraceptives, injectable progesterone, progestin sub-dermal implants, progesterone-releasing IUDs)
- Placement of a copper-containing intrauterine device (IUD)
- Condom with spermicidal foam/gel/film/cream/suppository
- Male partner who has had a vasectomy for at least 4 months
- Tubal ligation
- Hysterectomy

5. STUDY VISIT PROCEDURES

All study visit procedures should be conducted in the order listed in Section 5.1.

Informed Consent: Properly executed informed consent (written and verbal) is to be obtained prior to completion of any study-related procedures. Subjects must review, sign, and date the informed consent document and receive a copy. The original document should be retained in the Investigator's Site File (ISF) or with the Subject's source documents.

Medical and Ocular History: Relevant and clinically significant medical and ocular history must be recorded. This includes reported changes between Screening Visit 1 and first IP administration.

Concomitant Medications/Procedures: All prescription and over-the-counter (OTC) medications and nutritional supplements taken during the study and 30 days prior to the Screening Visit will be recorded. Additionally, all ocular hypotensive medications taken within 45 days prior to the Screening Visit will be recorded. Diagnostic and anesthetic eye drops do not need to be recorded. All procedures occurring during the study and 30 days prior to the Screening Visit will be recorded.

Randomization: Randomization will be accomplished using an Interactive Web Response System (IWRS). Site personnel will receive instruction about IWRS access and use.

Adverse Events: Any events occurring after the first dose of IP will be recorded as an adverse event. At each visit, the subject should be asked questions such as, "How are you feeling? How are your eyes feeling today? Have you had any changes since the last exam?"

IP Administration and Compliance: The first dose of study IP will be administered by study staff after the IOP measurement at T₀ on Day 1. Subjects will self-dose for the remainder of the trial except on study visit days when subjects will be instructed to refrain from self-dosing prior to the visit and the study morning IP will be administered by the unmasked dosing coordinator after the related IOP measurements; evening IP will be self-dosed (out of view of study staff) after the related IOP measurements. Compliance will be assessed at applicable visits by asking the subject their recollection of any missed doses. Confirmation of compliant IP dosing the evening prior to a study visit must be confirmed or the visit should be rescheduled. If the subject reports missing more than 4 doses since the prior visit, a Protocol Deviation will be documented and the subject will be counseled on IP compliance.

Heart Rate and Blood Pressure (BP) Measurements: Both systolic and diastolic blood pressure should be recorded. The same type of device and cuff must be used throughout the study on the same subject. An appropriate cuff size with a bladder encircling at least 80% of the upper arm should be used to ensure accurate measurements.

Blood pressure will be measured using the most ideal conditions possible given the subject's medical condition and age. If possible, the same arm should be used throughout the study. Blood pressure should be measured after sitting in a seated position for 5 minutes. Heart rate measurements will be measured by radial pulse for at least 30 seconds. The subject should be in a seated and relaxed state. An automated blood pressure unit may be used to measure the heart rate.

Best-Corrected Visual Acuity (ETDRS): Visual acuity will be performed before implementing any procedure that can affect vision (i.e., pupil dilation, tonometry, and gonioscopy). The most current refraction within 6 months prior to the Screening Visit will be recorded unless changes in refraction are suspected. If changes are suspected since the most current refraction, refraction should be repeated at the Screening Visit. The same optotype should be used throughout the study for a specific subject, and the right eye should be tested first. Best corrected visual acuity (BCVA) should be recorded using the ETDRS chart (or a modified ETDRS chart). If a change in BCVA is noted, pinhole may be used to test for the BCVA, but a formal refraction prior to dilation should be performed during that visit and/or on the next visit. The logarithm of the minimum angle of resolution (LogMAR) scores will be calculated according to the standard scoring methodology. A change of ≥ 10 letters may indicate an adverse event and should be investigated further by the investigator and the refraction should be rechecked.

ETDRS Scoring Methodology: The best-corrected visual acuity will be measured using an ETDRS (Early Treatment Diabetic Retinopathy Study) chart. The test distance must be at the distance specified on the ETDRS chart.

Position the ETDRS chart at the approximate eye level of an average-height seated subject. Mark a spot on the floor (e.g., with tape) that is the appropriate test distance from the ETDRS chart. The test distance and lighting for the chart must be kept constant throughout the study. The subject should be seated comfortably, directly in front of the chart, so that the eyes remain at the appropriate distance specified by the ETDRS chart. Testing always begins with the right eye, followed by the left eye. The fellow eye should be occluded.

Do not point to specific letters on the chart during the test. Ask the subject to read each letter slowly, line by line, left to right, beginning with Line 1 at the top. Tell the subject that the chart has letters only, no numbers. If the subject reads a number, remind him/her that the chart contains no numbers, and request a letter in lieu of the number. The subject should be told that only one chance is given to read each letter, but he/she may change his/her mind before moving to the next letter. Do not allow the subject to proceed to the next letter until he/she has given a finite answer. If the subject is unsure about the identity of the letter, then the subject should be encouraged to guess. The subject should be encouraged to continue reading even if making

mistakes. When a subject reaches a level where he/she cannot guess, the examiner may stop the test.

Each letter read correctly is counted. The examiner will total each line and the whole column (0 if no letters are incorrect) on the data collection form and record in the format specified.

Slit Lamp Biomicroscopy: This will be performed by the investigator's usual clinical technique and must be performed prior to pupil dilation OU. Changes and/or abnormalities of the anterior segment in the lids, conjunctiva, cornea, anterior segment, and lens will be graded. Iris color will be recorded at screening. Magnification, lighting, and examiner should be consistent for each subject throughout the study. Findings will be graded according to the following scales:

LID

Ervthema

None (0) Normal, without any redness, or less than mild

Mild (1+) A low grade flushed reddish color

Moderate (2+) Diffused redness encompassing the entire lid margin

Severe (3+) Deep diffused reddish color of lid margins and superior or inferior eyelid

Edema

None (0) Normal, no swelling of the lid tissue, or less than mild

Mild (1+) Slight diffuse swelling above normal

Moderate (2+) General swelling

Severe (3+) Extensive swelling of the eyelid(s), with or without eversion of upper and/or

lower lids.

CONJUNCTIVA

Hyperemia

None (0)
Normal: few vessels of bulbar conjunctiva easily observed
Minimal (0.5+)
Trace flush, reddish-pink color of the bulbar conjunctiva
Mild (1+)
Mild flush – Reddish pink of the bulbar conjunctiva
Moderate (2+)
Moderate, Bright reddening of the bulbar conjunctiva

Severe (3+) Deep, severe, bright and diffuse reddening of the bulbar conjunctiva

Edema

None (0) Normal, no swelling of the conjunctiva or less than mild Mild (1+) Slight diffuse or regional swelling of the conjunctiva

Moderate (2+) General swelling of the conjunctiva Severe (3+) Extensive swelling of the conjunctiva

CORNEA

Edema

None (0) Transparent and clear or less than mild

Mild (1+) = Dull glassy appearance

Moderate (2+) Dull glassy appearance of epithelium with large number of vacuoles Severe (3+) Epithelial bullae and/or stromal edema, localized or diffuse, with or without

stromal striae

ANTERIOR CHAMBER

Cells

None (0) No cells seen or less than mild

Mild (+ 1) 1-5 cells Moderate (2+) 6-10 cells Severe (3+) 11-20 cells

Hypopyon (4+) > 20 cells, Hypopyon Formation (indicate size of hypopyon)

Flare

None (0) No Tyndall effect or less than mild

Mild (1+) Tyndall beam in the anterior chamber has a mild intensity Moderate (2+) Tyndall beam in the anterior chamber is of strong intensity

Severe (3+) Tyndall beam is very intense. The aqueous has a white, milky appearance

LENS

Phakic Yes/No Aphakic Yes/No Pseudophakic Yes/No

For phakic only

Crystalline Lens

Normal (0) No opacity in the lens

Abnormal

Nuclear Cataract

None (0)

Minimal (1+) Minimal changes in nuclear zone

Mild (2+) Mild opacity with central zone still distinguishable

Moderate (3+) Moderate opacity
Severe (4+) Dense opacity

Cortical Cataract

None (0)

Minimal (1+) <1/8 of the circumference

Mild (2+) <1/8, but less than 1/4 of the circumference Moderate (3+) <1/4, but less than 1/2 of the circumference

Severe (4+) $\geq 1/2$ of the circumference

Posterior Subcapsular Cataract

None (0) Minimal (1+) Mild (2+) Moderate (3+) Severe (4+)

For pseudophakic only

Posterior capsular opacification (PCO)

None (0)

Trace/Mild (1+) <2 mm

Moderate (2+) $\geq 2 \text{ mm}$, but $\leq 3 \text{ mm}$

Severe (3+) $\geq 3 \text{ mm}$

Clear central axis (s/p YAG Capsulotomy)

Conjunctival Hyperemia: Hyperemia will be assessed and recorded separately from biomicroscopy through direct visual observation using photographic reference scale prior to fluorescein instillation and IOP measurement. The hyperemia will be graded on a 0 to 3 scale using the photographic reference scale provided by the Sponsor for use in this protocol.

- Normal: few vessels of bulbar conjunctiva easily observed
- 0.5 Trace flush, reddish-pink color of the bulbar conjunctiva
- 1 Mild flush Reddish pink of the bulbar conjunctiva
- 2 Moderate, Bright reddening of the bulbar conjunctiva
- 3 Deep, severe, bright and diffuse reddening of the bulbar conjunctiva

Tonometry (Intraocular Pressure): All IOP measurements must be measured by Goldmann applanation tonometry. The tonometer calibration should be checked for accuracy within one month before screening the first subject for the study. A Tonometer Calibration Form must be completed and filed before the first subject is screened and calibration must be checked monthly throughout the study. Variation within ± 2 mm Hg is acceptable. The fluorescein and anesthetic agents should remain consistent throughout the study. IOP will be measured following slit lamp biomicroscopy and always prior to dilation.

Two consecutive IOP measurements should be taken for each IOP time point, with the right eye being measured first. The applanation probe should be withdrawn between measurements. Intraocular pressure will be measured 2 times and the average will be used for analysis. If the two measurements differ by more than 2 mmHg, a third measurement will be taken and the median value will be used for analysis. Mean IOP values should be rounded up to the next whole number if the value is equal to or greater than 0.5 mmHg, and rounded down if less than 0.5 mmHg (e.g., 24.5 should be rounded to 25, 24.4 should be rounded to 24). The same procedure will be repeated on the contralateral eye.

In order to minimize confounding variables, every effort should be made to acquire all IOP measurements for each subject using the same tonometer and approximately at the same time at all visits. Every effort should be made to use the same examiner for each unique timepoint.

Pachymetry: Pachymetry will be performed OU at the Screening Visit; results obtained within the prior 6 months may be used if no change is suspected. Central corneal thickness (central zone) will be measured with a calibrated ultrasound pachymeter in both eyes after topical anesthetic has been applied. The subject will be in a seated position and fixating on a target straight ahead. Three measurements will be taken in the right eye first, and the average will be recorded in micrometers (μm). The same procedure is then performed on the left eye.

Gonioscopy: The gonioscopy examination will be performed OU at the Screening Visit; results obtained within the prior 6 months may be used if no change is suspected. Gonioscopy should be performed prior to instillation of dilating or miotic drops, with high magnification, and with dim illumination to potentiate visualization of the angle in its natural configuration. The angular width of the angle recess will be graded as an average score representative of all 4 quadrants using the grading criteria below.

Grade Description (Shaffer System, based on the angular width of the angle recess [Marsh & Cantor, 2005])

- 4 45 to 35° angular approach, wide open
- 3 35 to 20° angular approach, wide open
- 2 20° angular approach, narrow
- 1 $\leq 10^{\circ}$ angular approach, extremely narrow
- Slit 0° angle, narrowed to slit

Visual Field Examination: A visual field will be performed OU at the Screening Visit; reliable results obtained within the prior 6 months may be used if no change is suspected. Visual fields must be automated threshold visual fields (i.e., Humphrey [30-2 or 24-2] or Octopus equivalent).

SITA Standard (24-2 or 30-2) is preferred, SITA fast is also allowed. The subject's best correction at 33 cm is to be used. Visual fields must be reliable, defined as those with a) fixation losses less than or equal to 33%, b) false positives less than or equal to 33% and c) false negatives less than or equal to 33%. Visual fields are to be performed with a non-dilated pupil unless, in the opinion of the investigator, the pupil is so miotic (i.e., < 3 mm) that dilation is required. If the visual field examination was conducted using dilation at the Screening Visit, dilation should be used for any subsequent visual field examinations (i.e., if performed at an unscheduled visit; visual field testing should be performed during the trial if glaucomatous progression is suspected). Visual field interpretation must be documented and reviewed by the investigator, including an assessment of whether the results are normal or abnormal and the clinical significance of abnormalities.

Dilated Ophthalmoscopy: Posterior segment exam will be performed according to the investigator's preferred procedure. Magnification, lighting, and examiner should be consistent for each subject throughout the study. Ophthalmoscopy should be performed after pupil dilation (e.g., 1% tropicamide or cyclopentolate and/or 2.5% phenylephrine). The examination should include an evaluation of the vitreous, retina, macula, choroid, and optic nerve (including the absence or presence of notches and/or disc or peripapillary hemorrhages). Abnormalities and pathologic findings will be graded. Ocular structures will be graded according to the following scale.

Vitreous, Retina, Macula and Choroid: Examination emphasizes the visual axis.

- 0 Normal
- 1 Abnormal, describe.

Optic Nerve

- 0 Normal. No damage
- 1 Mild optic nerve damage, secondary to glaucoma including any rim loss (sloping or thinning)
- 2 Moderate optic nerve damage, including cupping to disc margin at one or more points
- 3 Severe optic nerve damage, nearly total cupping, only nasal rim or less present

Any new findings (i.e., notch and/or peripapillary hemorrhage) or deterioration occurring after the first IP dose will be reported as an adverse event. The cup/disc ratio will be recorded horizontally and vertically for each examination, and reported in 0.1 increments. Changes observed between Screening Visit 1 and prior to the first IOP dose will be reported as ocular history.

Pregnancy Test:

Urine pregnancy testing will be required at the Screening Visit for subjects of child-bearing potential and at Day 0. Pregnancy test results must be negative for subjects to continue in the study. On Day 28, a urine pregnancy test will be administered.

